4. LIST OF ABBREVIATIONS AND TERMS

AE	Adverse event
ALT	Alanine aminotransferase
API	Active Pharmaceutical Ingredient
AST	Aspartate transaminase
ARO	Arrowhead Pharmaceuticals, Inc.
AUC	Area under the curve
AUC _{inf}	Area under the curve from time 0 to infinity
BAL	Bronchoalveolar lavage
BP	Blood pressure
cGCP	current Good Clinical Practice
cGMP	current Good Manufacturing Practice
C _{max}	Concentration maximum (peak)
CRA	Clinical Research Associate
CRF	Case Report Form
CRO	Contract Research Organization
CTN	Clinical Trial Notification
CVA	Cerebrovascular accident
dL	deciliter
DSC	Data Safety Committee
EC	Ethics Committee
ECG	Electrocardiogram
eCRF	Electronic Case Report Form
EOS	End of Study
FDA	Food and Drug Administration
FEV1	Forced Expiratory Volume in the first second
FSH	Follicle-Stimulating Hormone
GCP	Good Clinical Practice
GGT	Gamma glutamyl transferase
GLP	Good Laboratory Practice
GMP	Good Manufacturing Practice
HBV	Hepatitis B virus
HIV	Human Immunodeficiency Virus
HR	Heart Rate
ICH	International Conference on Harmonisation
IRB	Institutional Review Board
IWRS	Interactive web response system
Kg	Kilogram
L	Liter
LLN	Lower limit of normal
MCH	Mean Cell Hemoglobin
MCHC	Mean Cell Hemoglobin Concentration
MCV	Mean Cell Volume
MedDRA	Medical Dictionary for Regulatory Activities
Mg	milligram
mmHg	millimeters of mercury

NHV	Normal healthy volunteers
NOAEL	No observed adverse event level
NYHA	New York Heart Association
PBO	Placebo
PD	Pharmacodynamic
PI	Principal Investigator
PK	Pharmacokinetic
ppFEV1	Percent predicted FEV1
PT	Prothrombin Time or Preferred Term
PTT	Partial thromboplastin time
QRS	QRS duration (complex) – a structure on the ECG that corresponds to the depolarization of the ventricles
QT	QT interval – a measure of the time between the start of the Q wave and the end of the T wave in the heart's electrical cycle
RDD	Respirable delivered dose
RNA	Ribonucleic acid
RNAi	RNA interference
SAE	Serious Adverse Event
SD	Standard Deviation
siRNA	Short interfering RNA oligonucleotides
SOA	Schedule of Assessments
SOC	System Organ Class
$t_{1/2}$	terminal elimination half-life
TIA	Transient Ischemic Attack
ULN	Upper Limit of Normal

5. INTRODUCTION

5.1. Background Information

Cystic fibrosis (CF), is caused by mutations in the CF transmembrane conductance regulator (CFTR) gene, which encodes a chloride and bicarbonate ion channel expressed at the apical surface of epithelial cells (Choi 2001; Stoltz 2015). In its wild-type form, the CFTR protein is localized on the cell surface and acts as a cyclic adenosine monophosphate (cAMP)-regulated ion channel (Alton 2016). The transport of anions (such as chloride and bicarbonate) through the apical membrane of epithelial cells creates an osmotic gradient for fluid secretion (Quon 2016). In the lungs, the balance of chloride ion secretion through functional CFTR protein and sodium absorption through the epithelial sodium (Na⁺) channel (ENaC) maintains an optimum volume, electrolyte composition, and pH of the airway surface liquid (a thin fluid layer protecting the epithelium from inspired air) (Hobbs 2013; Stoltz 2015; Vallières 2014). The CFTR protein also plays an absorptive role in some epithelial structures, particularly exocrine glands, such as the sweat gland, pancreas, gastrointestinal tract, and in the male and female reproductive tract. The absence or dysfunction of the CFTR therefore results in dehydrated, thickened secretions that obstruct these epithelium lined ducts of exocrine tissues, resulting in predisposition to infection, inflammation and tissue damage (Quon 2016).

As ENaC is negatively regulated by CFTR, reduced functional levels of or the absence of CFTR in patients with CF results in reduced chloride/bicarbonate ion and water secretion. Reduced CFTR function leads to ENaC hyperactivity, resulting in increased sodium ion and water absorption (Bangel-Ruland 2015; Hobbs 2013; Stoltz 2015) which subsequently contributes to dehydrated, thickened mucus. The combined effects of reduced chloride secretion (CFTR dysfunction) and hyperabsorption of sodium and water (ENaC hyperactivity) are dehydration of the cell surface, a reduction in the water content of the airway surface liquid, and thick, obstructive mucus that is resistant to removal (Stoltz 2015; Amaral 2015). Homeostasis of the airway surface liquid with adequate mucus hydration is essential for efficient mucociliary clearance of aerial pathogens, which is needed to maintain the sterility of the lung (Hobbs 2013; Stoltz 2015; Vallières 2014). Overly viscous and dehydrated mucus leads to impaired mucociliary clearance, resulting in infective/inflammatory sequelae, including airway mucus obstruction and disseminated bronchiectasis, recurrent bacterial infections, chronic inflammation, and lung damage/scarring (CFF Patient Registry Annual Report 2015; Maselli 2017). Finally, this cascade leads to end-stage lung disease, which can only be resolved by lung transplantation (Amaral 2015). Even in the setting of CFTR modulator/corrector therapy, there remains an unmet medical need for additional therapeutic options, particularly in certain sub-populations (e.g. those with Class I mutations). Additionally, ENaC inhibition may work synergistically with CFTR modulation (See Section 5.2.3).

5.2. Mechanism of Action of ARO-ENaC & Therapeutic Rationale

[figure not shown]
5.2.1. siRNA Mechanism of Action

RNAi-based therapeutics have the potential to silence the expression of any gene. RNAi is a naturally-occurring phenomenon by which short interfering RNA oligonucleotides (siRNAs) trigger a sequence-specific down-modulation of gene expression. RNAi triggers refer to synthetic siRNAs designed to target specific gene expression (Fire 1998).

ARO-ENaC is a synthetic, double-stranded, pulmonary epithelium-targeted RNAi trigger designed to specifically silence mRNA transcripts encoded by the α ENaC gene using an RNA interference mechanism. The RNAi trigger is a short, double-stranded RNA conjugated to an $\alpha\beta\delta$ integrin targeting ligand for the $\alpha\beta\delta$ receptor known to be present on the pulmonary epithelial cells. This targeting approach induces epithelial cell receptor-mediated endocytosis and introduction of the

double stranded RNAi trigger into the cytoplasm of epithelial cells which results in its association with the protein components of the RNA induced silencing complex (RISC), resulting in “on target” highly sequence-specific degradation of messenger RNA complementary to the antisense strand of the RNAi trigger. ARO-ENaC targets the α ENaC mRNA. Active RISC is a multiple turnover enzyme complex, therefore, incorporation of a single RNAi trigger into RISC can result in the degradation of many mRNA molecules, and subsequently, prolonged reduction of the expression of the corresponding protein. The persistence of pharmacologic activity significantly beyond the period of plasma or local tissue exposure is due to this unique RNAi mechanism in which a small amount of guide strand can persist and be active within RISC in the cytoplasm of target cells for extended periods of time.

siRNA mechanism of action

5.2.2. ENaC Inhibition

By delivering RNAi triggers targeting the α ENaC sequences to the pulmonary epithelium, it is possible to knock down expression of α ENaC mRNAs in pulmonary epithelial cells and thus reduce the number of active ENaC channels on the epithelial cell.

Reduced ENaC channel activity, should lead to improved hydration and mucus clearance in patients with CF. Since mucus dehydration and impaired mucociliary clearance results in infective/inflammatory sequelae, including airway mucus obstruction and disseminated bronchiectasis, recurrent bacterial infections, chronic inflammation, and lung damage/scarring in

patients with CF, improved mucus hydration and clearance is expected to prevent further pulmonary injury and allow for a reduction in CF induced sequelae. This therapeutic rationale is supported by human genetics where CF patients who are deficient in CFTR function (F508del mutations) but also harbor an ENaC loss-of-function mutation have milder CF symptoms compared to those with wild type ENaC and are reported to live into their 5th or 6th decade. (Agrawal 2017). Patients with normal CFTR function but with an ENaC activating mutation have a CF like phenotype (Rauh 2010). Additionally, patients homozygous for ENaC loss-of-function mutations have been shown to have enhanced mucociliary clearance relative to non-carriers (Kerem 1999). Such genetic target validation has inspired development of inhaled small molecule ENaC inhibitors which have been investigated in clinical trials. However, systemic absorption via the lung has caused discontinuation of small molecule studies secondary to renal uptake of small molecules by the distal tubule leading to dose limiting hyperkalemia in some studies (O’Riordan 2014).

The RNAi trigger in ARO-ENaC was designed to specifically target only the α ENaC mRNA. siRNA is poorly absorbed by most cell types without an appropriate surface receptor targeting ligand to induce endosomal uptake. Thus, uptake by non-pulmonary epithelial cells, such as cells in the renal distal tubule or collecting duct is not likely. In contrast to small molecule ENaC inhibitors, localized inhaled nebulized delivery of siRNA has shown very minimal systemic uptake with the majority of delivered drug remaining in the lung. Additionally, intravenous delivery of ARO-ENaC also does not induce significant ENaC gene silencing in the kidney and with both nebulized and intravenous delivery, no hyperkalemia has been seen in non-clinical studies (See Investigator’s Brochure).

5.2.3. Combining ENaC Inhibition with CFTR Modulators

Even in the setting of broadly used CFTR modulators, there remains an unmet medical need in CF patients. CF related exacerbation rates, which are important clinical events associated with disease progression, remain a significant issue even in patients receiving CFTR modulator therapy (Middleton 2019). Patients with high unmet need include those for whom no CFTR modulator therapies are available, those who are unresponsive to CFTR modulators due to their underlying mutations (approximately 10% of the CF population), those who require frequent hospitalization due to CF-related exacerbations, and those who do not tolerate inhaled antibiotics. There is a strong rationale for the potential of synergistic effects of ENaC inhibition and CFTR modulators in the 90 % that respond to elexacaftor/tezacaftor/ivacaftor. The rescue of CFTR by modulators is not perfect (~50% at functional level) and based on physiology, inhibition of ENaC is predicted to hyperpolarize the cell membrane potential and thus increase the driving force for chloride secretion via modulator-rescued mutant CFTR. Therefore, even patients for which CFTR modulator therapy is available are expected to have additional benefit from the development of new “add-on” therapies (Mall 2019).

ENaC inhibition may act synergistically with CFTR modulators. CFTR can secrete or absorb Cl⁻ across epithelial surfaces depending on the driving force that is determined by i) the intra- and extracellular Cl⁻ concentrations that are tightly regulated and result in a Nernst potential for Cl⁻ in the range of -30 mV in airway epithelial cells, and ii) the membrane potential of the cell that is set by the relative conductances of Cl⁻, Na⁺ and K⁺ channels and respective intra- and extracellular concentrations of these ions (Boucher 1994; Boucher 1994; Willumsen 1989). It is therefore predicted that if ENaC is inactive or not expressed in the same cell, cAMP-mediated stimulation will lead to a concomitant activation of apical CFTR and basolateral K⁺ channels that drives the membrane potential more negative than the Nernst potential of Cl⁻, and thus generate a driving force for CFTR-mediated Cl⁻ secretion. However, if ENaC is active in the same cell, this will depolarize the membrane potential, reduce the driving force for Cl⁻ secretion, and may even result in CFTR-

mediated Cl⁻ absorption as observed in the sweat duct (Boucher 1994; Boucher 1994; Willumsen 1991; Willumsen 1989; Greger 1996; Quinton 1983). The implications of these physiological findings on the combination of CFTR modulators and ENaC inhibitors in patients with CF are that inhibition of hyperactive ENaC in the apical membrane of airway epithelial cells may not only block ENaC-mediated Na⁺/fluid absorption, but will also hyperpolarize the apical cell membrane and thus increase the driving force for Cl⁻/fluid secretion via mutant CFTR channels that have been rescued and inserted into the apical plasma membrane in the setting of CFTR modulator use. Whether this results in synergistic effects on airway surface hydration, MCC and pulmonary outcomes in patients with CF and other muco-obstructive lung diseases needs to be assessed in clinical trials. However, there is a plausible scientific rationale for synergistic effect when using CFTR modulators with ENaC inhibition.

5.3. ARO-ENaC Pre-Clinical Pharmacology Studies

Further information on the pre-clinical pharmacology studies in monkey, rodent and sheep models is provided in the Investigator's Brochure.

5.4. ARO-ENaC Pre-Clinical Pharmacokinetic and Product Metabolism Studies

PK parameters for ARO-ENaC have been evaluated in multiple species. Results of these studies can be found in the Investigator's Brochure.

5.5. ARO-ENaC Pre-Clinical Toxicology Studies

ARO-ENaC has been clinically well tolerated in rats and in non-human primate toxicology studies. Details regarding GLP and non-GLP toxicology results are provided in the Investigator's Brochure.

5.6. Rationale for the Study

AROENAC1001 is a first in human dose-ranging study to assess the safety and tolerability of ARO-ENaC in healthy volunteers and in patients with CF. Arrowhead follows general principles of EMA and FDA guidance which indicate first-in-human (FIH) studies should initiate in healthy volunteers unless the drug is known or suspected to be unavoidably toxic or associated with a high degree of toxicity (e.g. chemotherapy or other oncology compounds). This is not the case with ARO-ENaC based on GLP toxicology results (See Investigator's Brochure).

Arrowhead believes valuable scientific information will be gained from the initial NHV component of the AROENAC1001 study. For example, healthy volunteers provide valuable tolerability and PK information in the absence of disease and can provide information that can be used for comparative purposes to patient groups. Additionally, results of a FIH study in CF patients may be difficult to interpret for the following reasons:

1. CF patients as part of their underlying disease may have fluctuations in labs (e.g. ALT and AST) and pulmonary status. These factors make initial safety data interpretation difficult and support initial first in man evaluation in an NHV population with minimal co-morbidities, normal lung function and normal laboratory values at baseline. Based on the GLP toxicology results, ARO-ENaC should be appropriately safe for healthy volunteers.
2. CF patients are commonly on concomitant medications for the treatment of CF and other co-morbid conditions. It would be beneficial to initially study ARO-ENaC in a healthy volunteer population not confounded by additional medications.

For these reasons, the study initiates in healthy volunteers and pending safety evaluation in NHVs, also enrolls CF patients. Treatment with ARO-ENaC is expected to reduce pulmonary epithelial ENaC channel density via RNAi. The magnitude of the reduction and duration of effect will depend on the dose. Since there has not been human clinical exposure to ARO-ENaC, an effective therapeutic dose to administer to patients with CF in later stage efficacy studies is unknown. Thus, the study plans to dose escalate in NHVs and will also evaluate multiple dose levels in CF patients.

The study begins with single dose cycle administration to healthy volunteers to evaluate ARO-ENaC for the purpose of understanding safety profile. There are no known serum biomarkers of ENaC; thus to gauge pharmacodynamic response in NHVs bronchoscopy with bronchial brushing and bronchoalveolar lavage (BAL) is planned to obtain airway epithelial cells (from brushing) and airway exosomes (from BAL) for analysis of α ENaC expression. Serum electrolytes will be monitored carefully with particular attention to potassium levels.

CF patients will require multiple doses of ARO-ENaC to sustain gene target silencing. Accordingly, this study uses a multiple-ascending dose (MAD) design to determine the dose required to reach and sustain maximal knockdown in pulmonary epithelial ENaC levels, and the dose-response relationship in patients with CF. There is no readily measurable serum assay for ENaC gene target silencing in humans. However, FEV1 and Lung Clearance Index have been used and well validated in multiple CF studies as potential markers of drug efficacy. LCI is time consuming in subjects with ppFEV1 < 70%; for feasibility reasons in CF cohorts 2b-4b, LCI will only be performed in subjects with ppFEV1 > 70% and CF cohort 4b will be restricted to subjects with ppFEV1 > 70% to allow for LCI assessments of all subjects in that cohort. CF cohort 6 will trial a different approach, with LCI assessments in all subjects, even in those with ppFEV1 < 70%.

CF cohort 6 is included in the study in order to assess the safety and efficacy of an alternate dosing regimen in CF patients. In this cohort, patients will be dosed on Days 1, 15, and 29, as opposed to Days 1, 2, 3 and 22, 23, 24 as in other CF cohorts. The respirable delivered dose (RDD, which is the amount of drug that reaches the lung, as opposed to the amount of drug loaded in the nebulizer) given on Day 1 to subjects in cohort 6 will be equal to or less than the total cumulative RDD given over Days 1, 2, and 3 to subjects in CF cohort 4b (which is the cohort receiving the highest dose level among CF cohorts 2b, 3b, 4b). The rationale for testing this dosing regimen is that sheep pharmacology studies indicate similar efficacy of ARO-ENaC when given via one single, larger dose as when given via three smaller daily doses. Additionally, sheep studies indicate a waning of drug effect at 3 weeks post-dose, providing the rationale for testing a 2 week dosing interval.

5.7. Risk Assessment for Participants

- **Embryo-Fetal:** Limited GLP toxicology studies have been conducted. Accordingly, eligible participants enrolled in this study, both male and female (including partners), must agree to use two highly effective forms of contraception during the study and for 3 months post-dose, or agree to abstinence (acceptable only if this method is in alignment with the normal lifestyle of the patient).
- **Electrolyte Disturbances:** Small molecule inhibitors of ENaC have been associated with mild hyperkalemia (O’Riordan 2014). This was due to systemic absorption of the small molecule inhibitors with ENaC inhibition in the kidney distal tubule leading to potassium reabsorption. ARO-ENaC has not been shown to produce hyperkalemia in various GLP toxicology studies when administered via inhaled nebulized solution and even when administered intravenously.

Avoidance of renal ENaC inhibition and associated hyperkalemia is facilitated by local nebulized delivery and the poor uptake of siRNA molecules by cells lacking the appropriate receptor. Hyperkalemia is not expected in this study. However, frequent monitoring, avoidance of medications known to cause hyperkalemia, stopping rules for hyperkalemia and a hyperkalemia treatment guideline (Section 16.2) are utilized to mitigate risk.

- **Pulmonary:** GLP animal toxicology studies have not revealed evidence of pulmonary toxicity at clinically relevant doses and NOAELs from such studies provide a wide therapeutic index. However, as this is the first administration of ARO-ENaC in humans, careful monitoring of pulmonary function is prudent. Very frequent measurement and tracking of FEV1 as described in the SOA and stopping rules for adverse changes in lung function are intended to mitigate the risk of pulmonary toxicity.
- **Bronchoscopy:** This is a semi-invasive procedure involving sedation, local anesthesia and insertion of a bronchoscope into the airways. Following insertion of the bronchoscope, bronchoalveolar lavage and bronchial brushings will be performed; notably, no transbronchial biopsies will be taken. Bronchial brushings will be taken from the lung periphery under fluoroscopic visualization of brush location. Complications of bronchoscopy include sore throat, bronchospasm, hypoxemia, laryngospasm or laryngeal injury, fever, and adverse reactions to sedation. The most common adverse event is laryngospasm which occurs in 0.6% of flexible bronoscopies (Pue 1995). More severe complications such as pneumothorax and pulmonary hemorrhage are rare (0.1 to 0.2% for each) and occur more frequently in the setting of transbronchial biopsies, which will not be performed in this study (Pue 1995; Facciolongo 2009). Patient selection has a significant impact on procedural complications and the risks of bronchoscopy in normal healthy volunteers will be lower than in patients with underlying respiratory disease.

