6.2. Secondary Endpoints

1. Changes from pre-dose baseline in serum electrolytes in NHVs and CF patients as a safety measure.
2. Changes from pre-dose baseline in Forced Expiratory Volume (FEV1) in NHVs as a measure of safety.

3. Pharmacokinetics of ARO-ENaC in NHVs and in CF patients

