7.4. Stopping Rules & Data Safety Committee

A decision to stop the trial early or discontinue drug in an individual subject, group of subjects or to halt enrollment temporarily or permanently may be indicated based on any of the following:

1. A single Serious Adverse Event (SAE, defined in Section 11.1) considered at least possibly related to study drug
2. Two cases of a drop from baseline FEV1 (which must be confirmed on repeat within 48 hours) **in healthy volunteer cohorts** of $\geq 20\%$ (absolute decline in % of predicted) considered to be at least possibly related to study drug by study investigator
3. One case of a drop from baseline FEV1 (which must be confirmed on repeat within 48 hours) **in cystic fibrosis cohorts** of $\geq 20\%$ (absolute decline in % of predicted) considered to be probably related to study drug by study investigator.
4. A post-dose increase in serum potassium to > 5.7 milliequivalents/Liter which must be from a non-hemolyzed sample and confirmed by repeat blood draw within 48 hours of initial results.

If any such events occur, within 5 days of Sponsor being notified of the event, the DSC will meet to review the event and determine any necessary actions as detailed below. Further dosing of the subject who triggered the stopping rule will be paused until such DSC review occurs.

Central labs will be utilized. However local labs may be utilized as necessary (including for Screening) if needed by the investigator or for emergent situations, including time critical analytes such as serum potassium and repeat clinical chemistries.

The Sponsor or PI can discontinue any subject at any time with or without DSC consultation. If such events (as described above) occur and the subject is not discontinued from the study the reason for not discontinuing the subject will be included in DSC meeting minutes. Including, but not limited to the events listed above, the DSC may pause the study to additional dosing or dose escalation to provide time to evaluate safety data and recommend the action to be taken, which may include, but is not limited to one of the following:

- Discontinuation of a subject or group of subjects from the study
- The study is stopped immediately with no further dosing
- The study will continue until the current cohort is completed
- The study will continue, but the next dose escalation will be to a level midway between the current level and the next planned level
- The study will continue as planned

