- If a subject's Day 1 (pre-dose) baseline spirometry measurement is pre-bronchodilator but the subject fails to withhold bronchodilator on a subsequent visit day, then post-bronchodilator spirometry should be performed on that visit day only
- If a subject fails to withhold bronchodilator on the Day 1 (pre-dose) baseline spirometry measurement, then the Day 1 spirometry measurement should proceed as a post-bronchodilator measurement. Importantly, all subsequent spirometry measurements for that subject should also be performed post-bronchodilator
- Each spirometry assessment will be recorded in the source documents as pre- or post-

bronchodilator

Finally, the above considerations only apply to the initial spirometry assessment of a visit. On dosing days, subjects will also undergo repeat (post-dose) spirometry assessments. Those post-dose spirometry assessments may be either pre-bronchodilator or post-bronchodilator, which should be recorded in the source documents. In CF patients, the initial spirometry assessment of a visit will be used for efficacy assessments, while the post-dose spirometry measures will be used as safety assessments.

- **Cystic Fibrosis Questionnaire-Revised (CFQ-R):** The questionnaire provides information about demographics, quality of life and daily activities. Subjects will be asked to complete the CFQ-R in their native language if valid translations are available. If there is no validated translation then the subject will not complete the questionnaire. Copies of the CFQ-R will be provided in the study Procedural Manual.

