### **9.6.1 Spirometry**

Spirometry will be evaluated in NHVs and CF patients. In general, spirometry for NHVs are considered a safety measurement and spirometry for CF patients are considered both a safety and efficacy measurement. For CF patient cohorts, use of an inhaled bronchodilator will be recorded at each spirometry assessment. All CF patient spirometry summaries will identify use of an inhaled bronchodilator as recorded on the Spirometry eCRF.

---

Descriptive statistics summaries of pulmonary function parameters obtained from the spirometry assessments will be provided by scheduled timepoint. Absolute changes and percentage changes from baseline will be included. In addition to an overall summary, subgroup analyses (as defined in Section 4.2) will be provided.

A sensitivity analysis of FEV1 and ppFEV1 will be performed for CF patient cohorts if use of an inhaled bronchodilator at any post-baseline assessment does not match use of an inhaled bronchodilator at the baseline assessment for any CF patients. The sensitivity analysis will consist of a summary of FEV1 and ppFEV1 values with absolute and percent changes from baseline by scheduled visit, excluding any post-baseline spirometry assessments where the bronchodilator status does not match the bronchodilator status at baseline. Subgroup analyses will not be provided for the sensitivity analysis.

Plots of mean (+/- SD) FEV1 (L) and ppFEV1 (%) over time will be provided by study day from baseline to the EOS visit. Plots for CF patient cohorts will additionally include a plot from baseline to Day 37 (Cohorts 2b-4b) and a plot from baseline to Day 43 (Cohort 6).

Additionally, a plot will be provided for CF patient cohorts to visually assess the relationship between baseline sweat chloride level and ppFEV1 absolute change from baseline value. For Cohorts 2b-4b, the Day 37 ppFEV1 absolute change from baseline value will be used. For Cohort 6, the Day 43 ppFEV1 absolute change from baseline value will be used. Pearson correlation coefficients may be provided within the plot.

All pulmonary function data obtained from the spirometry assessment will be listed by subject.

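### SAP 9.6.1 tabulates spirometry only by scheduled timepoint, so no planned table counts subjects per arm who meet the protocol's per-subject 20-point ppFEV1 definition

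*Protocol*

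**What the plan says.** **The safeguard.** Protocol 5.7, under pulmonary risk, relies on "Very frequent measurement and tracking of FEV1 as described in the SOA and stopping rules for adverse changes in lung function". It gives no threshold. Protocol 7.4 (and the synopsis) does: an absolute decline of at least 20 points of percent predicted FEV1, confirmed on repeat within 48 hours. In healthy volunteers the trigger is two cases judged at least possibly related. In CF patients it is one case "considered to be probably related to study drug by study investigator".

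**FEV1 as a safety measure.** Protocol 6.2 lists as a secondary endpoint "Changes from pre-dose baseline in Forced Expiratory Volume (FEV1) in NHVs as a measure of safety". For CF patients, Protocol 10.3.7 says that "the post-dose spirometry measures will be used as safety assessments".

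**The analysis.** SAP 9.6.1 states: "Descriptive statistics summaries of pulmonary function parameters obtained from the spirometry assessments will be provided by scheduled timepoint". It adds absolute and percent changes from baseline, the same by subgroup, a bronchodilator-mismatch sensitivity summary for CF patients, mean plots and a sweat-chloride plot. It ends with a listing: "All pulmonary function data obtained from the spirometry assessment will be listed by subject". SAP 9.1 sets the statistics as n, mean, median, SD, minimum and maximum. SAP 7.1 refers back to the protocol for the stopping rules and plans no tabulation of subjects who meet them.

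**The concern.** The lung-function criterion asks a question about individuals: did this subject fall by 20 points or more, and was the fall confirmed? The planned tables answer a question about visits: what was the distribution of change at this timepoint? A column of by-visit rows cannot be converted into a number of subjects, because it does not show whether low values in different rows belong to one person or several.

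At stake is the between-arm view of large falls in ppFEV1. The stopping rule does not supply it, because it counts only falls that a blinded investigator attributes to drug, with a stricter attribution in CF patients than in healthy volunteers. The SAP already takes the subject-level view for laboratory data. SAP 9.5.2 plans shift tables from baseline to the worst post-baseline grade, potassium included (SAP Appendix A), and peak or lowest values for selected tests. Potassium and FEV1 both carry stopping rules in Protocol 7.4, but only potassium gets a per-subject worst-value table.

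**Working it through.** **1. The plan's own subject-level figure.** Protocol Table 5 sizes all cohorts except Cohort 6 on the chance of at least one subject with a TEAE, 1 - (1 - p)^n. For p = 0.3, n = 4: 1 - 0.7^4 = 0.7599, against 0.76 stated. For p = 0.2, n = 9: 1 - 0.8^9 = 0.8658, against 0.87. All 14 rows reproduce. Nothing here is disputed. It shows that the plan reasons about safety in subjects affected, which is the figure missing for FEV1.

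**2. Denominators.** SAP Section 9 groups by dose and regimen, with placebo pooled within each population.
- Healthy volunteers: active 4, 4, 4, 4 and 8 (Cohorts 4 and 5 merge to 12 if given the same dose); placebo 2 + 2 + 2 + 2 + 4 = 12.
- CF: active 4, 4, 9 and 18; placebo 2 + 2 + 3 + 6 = 13.

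**3. What a timepoint row shows.** Assume one subject falls 20 points and the others do not change. The row mean moves by -20/n: -5.0 with n = 4, -2.2 with n = 9, -1.1 with n = 18. Against the SD of 7 in Protocol 12.1, the last is 1.1/7 = 0.16 SD. The row minimum is -20 in every case, so the table shows that someone fell at that visit.

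**4. What the rows cannot show.** Take 18 active Cohort 6 patients and three visits, others unchanged.

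| Scenario | Mean change, each visit | Minimum, each visit | Subjects affected |
|---|---|---|---|
| Three subjects, one fall each, at different visits | -20/18 = -1.1 | -20 | 3/18 = 16.7% |
| One subject, a fall at all three visits | -20/18 = -1.1 | -20 | 1/18 = 5.6% |

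Every row holds seventeen zeros and one -20 in both scenarios, so n, SD, median and maximum also agree. The planned tables are identical while the incidence differs threefold.

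**5. Noise in a worst-of-many measure.** This is an illustration under strong assumptions: normal changes, SD 7 at every test, independent tests. The protocol gives the SD of 7 only for the Cohort 6 Day 43 change, and changes that share one baseline are not independent. Protocol Table 1.4 gives 18 post-baseline tests: 2 on Day 1, 3 each on Days 15 and 29, and 10 on other days.
- 20 points: Phi(-20/7) = 0.0021 per test; about 18 x 0.0021 = 3.8% per patient; chance that at least one of 18 patients is flagged, 1 - (1 - 0.038)^18, about 50%.
- 10 points: Phi(-10/7) = 0.077 per test; 1 - (1 - 0.077)^18 = 76% per patient, or about 14 of 18.

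A 20-point count is therefore usable if read against pooled placebo. A 10-point category would mostly record noise.

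**6. Unscheduled tests.** The 48-hour repeat decides whether a fall is confirmed, and the protocol also requires lung function testing when certain respiratory AEs occur. SAP 9.6.1 keys its tables to scheduled timepoints, so these tests are not clearly included.

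**The case against.** The strongest reply is that nothing is lost and no endpoint lacks an analysis. The healthy-volunteer endpoint is change from baseline, which the SAP summarises. The minimum change flags a 20-point fall at any scheduled timepoint. The listing holds every value, and with groups of 4 to 18 a hand count is feasible. Clinically significant abnormal assessments are recorded as AEs (Protocol 11.2), and SAP 9.5.1 tabulates TEAEs per subject by relationship and severity. The study is descriptive (SAP 2.2). All of this stands, and it limits the point to a reporting gap.

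Several stronger readings are tempting, and the documents do not support them:
- *The report cannot yield a count by arm, or falls judged possibly related in CF are counted nowhere.* The listing allows the first, and the AE tables capture the second when the fall is recorded as an AE. What is missing is a planned count on the 20-point definition that does not depend on the investigator's judgement.
- *A fall would be invisible.* That could be argued only of the mean in a large arm. The minimum shows it, and in a 4-subject arm the mean itself moves by 5 points.
- *Section 5.7 promises such a table.* It describes mitigation during the trial and contains no 20-point figure. Protocol 7.4 carries that mitigation out through committee review within 5 days, and the gap does not affect it.
- *Rare large falls are the expected form of toxicity.* The documents do not say so. Section 5.7 reports no evidence of pulmonary toxicity at clinically relevant doses in the GLP animal studies.

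The laboratory comparison is also not exact: the potassium shift table uses CTCAE grades, not the protocol's 5.7 mEq/L trigger. It still gives each subject's worst grade, which FEV1 lacks.

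**Conclusion.** The point holds as a gap in planned reporting. Protocol 7.4 sets a per-subject criterion, and SAP 9.6.1 plans neither a summary of each subject's worst ppFEV1 change nor a count by arm of subjects meeting the 20-point definition regardless of causality. The planned by-visit statistics can be identical for 3/18 and 1/18.

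That example assumes all other subjects are unchanged. It shows what the tables cannot separate and does not predict what will happen. The conclusion does not depend on the noise calculation, which bears only on the choice of threshold and on how to read the counts. The table shells are in a companion document that was not available, but SAP Section 1 describes them as formats for outputs in the SAP, so an additional table is not expected there. No sample size, power figure or clinical rule is affected. The improvement is modest and almost free.

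**What to change.** Add to SAP 9.6.1 one table for healthy volunteers and one for CF patients, by dose group and pooled placebo, giving:

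- (a) a descriptive summary of each subject's largest absolute fall in ppFEV1 from baseline over all post-baseline tests, stating that post-dose and unscheduled tests are included; and
- (b) n (%) of subjects with a fall of at least 20 points at any time, and the number confirmed on repeat within 48 hours, regardless of causality.

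Use the baseline already defined in SAP Section 5. Do not add a 10-point category. State that the counts are to be read against pooled placebo, because the worst of many tests picks up some noise.

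The cost is a short SAP addition and one extra table per population, from data already collected. The stopping rule and its review process stay as they are.
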